### 10.5.2 Duration of Response (DoR)

It is *defined as time from the initial response to documented disease progression.*

The DoR will be presented for patients with confirmed complete response or partial response.

This data will be summarized using the Kaplan-Meier method. Also, data will be displayed graphically for: PTCL subjects in dose escalation and dose expansion together, CTCL subjects in dose escalation and dose expansion together, and overall.

The patients who did not progress or die without disease progression will be censored at the date of their last disease assessment. The following reports will be generated:

- The Q1, median and Q3 DoR time will be provided along with 95% CI for the Q1, median, and Q3 DoR time will be presented using Brookmeyer-Crowley method (subject to availability of adequate data).
- The number and % of patients with progressive disease will be provided.
- The number and % of patients censored (further divided by reasons for censoring) will be provided.
- Kaplan-Meier curves will be produced.
- DoR data will be listed.

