3.1.2 Secondary Endpoints

- **Efficacy:**

1. **Objective Response Rate (ORR)**, defined as sum of CR and PR rates, assessed according to the Lugano Classification for initial evaluation, staging, and response assessment of Hodgkin/non-Hodgkin lymphoma in PTCL patients; and according to the modified Severity Weighted Assessment Tool (mSWAT) in CTCL patients.
2. **Duration of Response (DoR)**, calculated as time from the initial response to documented disease progression.

- **Pharmacokinetics:**

PK Parameters [AUC $(0-\infty)$, AUC $(0- t)$, C_{max} , t_{max} , K_{el} , and $t_{1/2}$] of Tenalisib and Romidepsin.

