8.2 Response Evaluations and Measurements

In all patients (PTCL and CTCL), the response will be assessed approximately at 8 weeks interval for the first two assessments [(e.g. C3D1 (\pm 7 days), C5D1 (\pm 7 days)] and then at C8D1 (\pm 7 days) and/ or at the EOT or as clinically indicated (if clinical progression is suspected).

- **PTCL**

PTCL patients will be evaluated according to Lugano classification Cheson 2014)^[16] ([Appendix C](#)) using the CT scan. PET-CT will be preferred for FDG-avid lymphomas. The modality chosen should be the same throughout the duration of the study. In addition, PET-CT will be performed at C3D1 (\pm 7 days) and to confirm CR. If PET and CT scan at Screening are negative for disease involvement in the neck, subsequent CT scans may not include neck. If PET and CT scans at Screening are positive for disease involvement of the neck, subsequent CT scans must include neck. Disease assessments and imaging should not be delayed for delays in cycle starts. Disease assessments and imaging should be continued until documented disease progression, the start of new anti-cancer treatment, withdrawal of consent, death, or the end of the study, whichever occurs first.

Each participating site will be responsible for radiological review and confirmation of response as per standard efficacy guidelines. The frequency outlined is the minimum required for study participation. Patients who progress according to the corresponding criteria will receive no further treatment. Patients who respond to the treatment (i.e., CR, PR or SD) may remain on trial. All disease specific assessments are to be completed as applicable to disease type.

- **CTCL:**

CTCL patients will be evaluated as per modified Severity Weighted Assessment Tool (mSWAT) ([Appendix F](#)).^[17] Additionally, CT scan will be done in the CTCL patients with lymph node and visceral involvement. CTCL patients with subcutaneous lesions which cannot be measured by mSWAT will be assessed by change in PET-CT avid lesions. Bone marrow biopsy will be performed in patients with B2 blood involvement. In these patients, Sezary cell count will be quantified by flow cytometry or morphology in blood/bone marrow.

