9.4.3 Efficacy analyses

The efficacy endpoints will include:

- ORR: The percentages of CR, CR+PR, and CR+PR+SD as well as Conversion Rate for Group 2 will be presented, as will the median duration of response. The 95% confidence intervals of these percentages may also be presented.
- DOR: DOR is defined as time from the initial response to documented disease progression. This variable will be analyzed via Kaplan-Meier methodology.

Additional analyses may also be performed as appropriate.

These analyses will be performed from time to time for presentation/publication purposes.

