### 10.5.3 Best Overall Response (BOR)

It is the best response, as assessed and confirmed by site PI, from the start of the treatment until disease progression or discontinuation from the study.

This data will be summarized using frequency and percentage for CR, PR, SD, and PD, as reported in the CRFs for overall subjects. This data will also be listed.

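### Duration of response ends only at documented progression, and the ambiguous censoring sentence in SAP 10.5.2 most consistently censors responders who die without it

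*SAP*

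**What the plan says.** Every definition of DoR names one end event. Protocol 3.1.2 has DoR "calculated as time from the initial response to documented disease progression", and SAP 4.2 repeats it. Protocol 9.4.3 says "DOR is defined as time from the initial response to documented disease progression", to be analysed by Kaplan-Meier, with no censoring rule. SAP 10.5.2 carries the same definition. Death is not named as an event in any of the four places.

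The only censoring rule is in SAP 10.5.2: "The patients who did not progress or die without disease progression will be censored at the date of their last disease assessment". The outputs listed there are of two kinds: "The number and % of patients with progressive disease will be provided" and "The number and % of patients censored (further divided by reasons for censoring) will be provided". The censoring reasons are not named.

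Two other protocol sections bear on deaths:

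- Section 8.2 treats documented progression and death as separate reasons to stop imaging in PTCL, which continues "until documented disease progression, the start of new anti-cancer treatment, withdrawal of consent, death, or the end of the study".
- Section 7.4.4 sends on-study deaths that the investigator puts down wholly to the lymphoma to the discontinuation form of the eCRF. It does not ask for an assessment that documents the progression.

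**The concern.** The censoring sentence can be parsed in two ways, and the two give different results for a responder who dies before progression is documented. Two programmers working from the same SAP could therefore produce different curves.

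The more consistent parse treats a responder who dies, for example of infection, as still in response when last assessed. That patient then leaves the risk set. DoR becomes time to documented progression with death censored. Its curve is more favourable than time in response and alive, which is what many readers take DoR to mean. DoR is a named secondary endpoint, and durability is part of the rationale for the combination (Protocol 1.3.2).

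A narrower gap concerns a death attributed to progression without Lugano imaging or an mSWAT assessment to document it. No sentence says expressly how it is handled or dated.

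**Working it through.** **1. The two readings.** The documents give no DoR median, event count or power, so there is no plan figure to reproduce. The first check is on the text.

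| | Reading 1 | Reading 2 |
|---|---|---|
| Who is censored | Patients who did not progress, and patients who die without progression | Only patients who neither progressed nor died |
| Death without documented progression | Censored at last assessment | Event |
| Fits the progression-only definition | Yes | No |
| Fits the two output counts | Yes | No, there is no count of death events |
| Fits the closing words on dying without progression | Yes | Poorly |

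Reading 1 is the more consistent. Under it, a death attributed to progression but never documented is not the defined event, so it too is censored by implication.

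**2. Timing.** The schedule tables put C3D1 on day 57 and C8D1 on day 197; C5D1 is day 4 × 28 + 1 = 113. For a response first seen at C3D1, C5D1 is day 113 − 57 = 56 of response and C8D1 is day 197 − 57 = 140. A death just before C8D1 is censored back by up to 140 − 56 = 84 days.

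**3. Effect of one death.** Suppose *n* responders are at risk just before the death and no event falls between the last assessment and the death. Then from the death onward:

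S(death as event) = S(death censored) × (n − 1)/n, so the gap is S(death censored)/n.

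If another responder's progression falls in that interval, the censored curve can sit slightly lower until the death. From the death onward it is the higher one.

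**4. Worked cases.** Assumed: 7 responders at C3D1 and one death on day 98 of response, last assessed on day 56. The number 7 is an assumption guided by the single-agent result in PTCL (7/15, Protocol 1.1.2).

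- Case A: 1 progression at C5D1, 2 at C8D1, 3 ongoing. Death censored: 6/7 × 3/5 = 51.4% at day 140, median not reached. Death as event: 6/7 × 5/6 × 3/5 = 42.9%, median 140 days. Gap 0.514/6 = 8.6 points.
- Case B: none at C5D1, 2 at C8D1, 4 ongoing. Death censored: 4/6 = 66.7%. Death as event: 6/7 × 4/6 = 57.1%. Gap 0.667/7 = 9.5 points. The median is not reached either way.

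Case A keeps a responder who progresses at the next assessment; Case B has every response holding at a second one.

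**5. Other responder counts.** Assumed: the single-agent response rate of 46% (Protocol 1.1.2) applied to 24 and 42 patients, 0.46 × 24 = 11.0 and 0.46 × 42 = 19.3; one death on day 100, last assessed on day 56.

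- 11 responders, 1 progression at C5D1 and 2 at C8D1: 10/11 × 7/9 = 70.7% against 10/11 × 9/10 × 7/9 = 63.6%.
- 19 responders, 2 at C5D1 and 3 at C8D1: 17/19 × 13/16 = 72.7% against 17/19 × 16/17 × 13/16 = 68.4%.

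**6. Average effect.** Assumed: independent exponential times, and a death hazard that is a fraction f = 0.10 to 0.25 of the progression hazard. The documents give no such rate. With months of 30.4375 days, S = 2^(−(140/30.4375)/median) and the gap is S − S^(1+f).

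- Median 13 months (the romidepsin DoR in Protocol 1.2, taken as a median): S = 0.7825, gap 1.9 to 4.7 points.
- Median 4 months (the floor in Protocol 1.3.2, taken as a median): S = 0.4507, gap 3.5 to 8.1 points.

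**7. Chance that it matters.** Under the same assumptions, the probability that a responder dies before progression by day 140 is f/(1+f) × (1 − S^(1+f)).

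- Lowest: 0.10/1.10 × (1 − 0.7636) = 0.0215.
- Highest: 0.25/1.25 × (1 − 0.3692) = 0.126.

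Among 7 responders that is 0.15 to 0.88 expected deaths, and a chance of at least one of 14% to 61%.

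**The case against.** The best defence is that progression-only DoR is a deliberate choice, stated identically in four places. The SAP tests no hypotheses (9.1), so no error rate or sample size depends on it. SAP 10.5.2 tabulates censoring reasons and lists DoR data, and SAP 10.6.2 summarises deaths. With so few responders a reader could recalculate the curve. The worked cases assume that a death occurs, which the hazard assumptions do not guarantee. All of this stands, and it limits the point to definition and reporting. It does not remove the double reading, and listing a death does not put it into the curve, the quartiles or their intervals.

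A reader might infer more than the documents support:

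- *That progression deaths without documentation have no status at all.* They are not named, but the definition requires documented progression, so they fall to censoring. What is missing is an express statement.
- *That such deaths are those without a scan.* CTCL response is assessed by mSWAT (Protocol 8.2), so the relevant gap is the lack of any documenting assessment.
- *That the Kaplan-Meier method is misapplied or deaths are concealed.* The estimator suits the stated definition, and the censoring reasons can show the deaths.
- *That one death will change the median.* It does in Case A and not in Case B.

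**Conclusion.** The point holds as a cheap improvement. SAP 10.5.2 has a censoring sentence with two readings. The more consistent one censors responders who die without documented progression, and at C8D1 the resulting estimate is at or above the progression-or-death estimate. In the one-death illustrations the gap at day 140 is 4.3 points with 19 responders (72.7 − 68.4), 7.1 with 11 (70.7 − 63.6), and 8.6 to 9.5 with 7. Averaged over the assumed death hazards it is 1.9 to 8.1 points. A single death can, but need not, decide whether a median is reached. The direction and the ambiguity follow from the text. The sizes rest on assumed responder counts, death rates and event times, none of which the plan gives.

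**What to change.** 1. Reword SAP 10.5.2 for the protocol-defined DoR so that it has one reading: *Responders without documented progression, including those who die without it, are censored at their last disease assessment.*
2. Beside it, add DoR to documented progression or death from any cause, whichever is first, with events split into progression and death. Count a death attributed to progression but lacking a documenting assessment (Lugano imaging or mSWAT) as an event on the date of death.
3. Use one cut-off for deaths and survivors: count only deaths on or before the C8D1 assessment, or the date it was due, and list later deaths separately. Otherwise a late death can fall after every living responder has been censored. For example, with 7 responders, 2 progressions at C8D1 and 5 ongoing, the estimate is 5/7 = 71.4% at day 140. If one of the five dies on day 160 and the other four were censored at C8D1, one patient is at risk and the curve drops to zero.
4. Show death as its own censoring reason in the progression-only analysis, and give numbers at risk.

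The cost is a few SAP sentences, one table and one curve. DoR will look slightly less favourable in the added analysis if such deaths occur. The protocol definition is kept, so comparability with Protocol 3.1.2 is not lost. Active follow-up after the last dose is a 30-day telephone contact (Protocol 6.13), so deaths of patients who stopped treatment early may be incompletely known; the report should say so.

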### 10.5.3 Best Overall Response (BOR)

It is the best response, as assessed and confirmed by site PI, from the start of the treatment until disease progression or discontinuation from the study.

This data will be summarized using frequency and percentage for CR, PR, SD, and PD, as reported in the CRFs for overall subjects. This data will also be listed.

## 10.6 Safety Analysis

### 10.6.1 Treatment Exposure and Compliance

Analysis set: Safety

The treatment exposure and Treatment compliance will be summarized descriptively (n, mean, median, standard deviation, minimum and maximum values) and will also be listed.

- The treatment exposure to the study medication for patient will be calculated as:

Exposure (day) = Last day of dosing – First Day of dosing + 1

- A summary of duration of treatment (days) will be provided. In addition, a swimmer plot for duration on treatment will be provided individually for the patients with PTCL, CTCL and Overall. The BOR (CR/ PR/ SD/ PD) obtained for each patient at Cycle 3 Day 1 efficacy assessment will be used for representing the responses for each patient in graphical representation.

- The treatment compliance as reported for each patient in the eCRF, will be summarized descriptively for each cycle. This data will be listed for individual patient.

Note: If the patient fails to return the study treatment on the scheduled return cycle, then that patient data will not be considered for calculating the compliance at the respective return cycle. This approach will be applied for both the summary table and the listing presentation of treatment compliance.

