5.5.1 Tenalisib

Subjects will be instructed to bring any unused study drug to the site at each visit. Research personnel will count and record the number of used and unused study drug tablets at each visit. The study coordinator will question the patient regarding adherence to the dosing regimen, record the number of tablets and strengths returned, the date returned and determine treatment compliance before dispensing new medication to the study patient. Compliance below 80% will require counseling of the patient by study site personnel.

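### SAP 10.6.1 drops Tenalisib cycles with no scheduled drug return from both the compliance table and the listing, so per-cycle compliance may be biased, more plausibly upward

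*SAP*

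**What the plan says.** SAP 10.6.1 bases compliance on the eCRF value, by cycle: "The treatment compliance as reported for each patient in the eCRF, will be summarized descriptively for each cycle". Exposure and compliance "will be summarized descriptively (n, mean, median, standard deviation, minimum and maximum values) and will also be listed".

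A Note then deals with drug that does not come back on schedule: "If the patient fails to return the study treatment on the scheduled return cycle, then that patient data will not be considered". The exclusion is limited to the cycle concerned: "that patient data will not be considered for calculating the compliance at the respective return cycle". On scope it adds: "This approach will be applied for both the summary table and the listing presentation of treatment compliance". The SAP gives no rule for tablets returned late, no count of the cycles left out and no sensitivity summary. SAP 9.3, on missing data, covers dates only.

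Protocol 5.5.1 describes how the data arise. "Subjects will be instructed to bring any unused study drug to the site at each visit", and "Research personnel will count and record the number of used and unused study drug tablets at each visit". The coordinator also asks about adherence, and Protocol 3.4.3.1 requires missed doses to be documented. On follow-up: "Compliance below 80% will require counseling of the patient by study site personnel". Romidepsin compliance is measured by number of infusions (Protocol 5.5.2), so in practice the Note affects Tenalisib only.

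**The concern.** Whether a patient brings drug back is plausibly related to how much was taken. A patient who has lost track of dosing, or who stops early because of toxicity or progression, may be less likely to return tablets at the planned visit. Leaving those cycles out makes the summary describe returned cycles only.

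The rule can also set aside usable data. The schedules of events (Protocol Tables 5 and 6) mark drug compliance at Days 8 and 15 of the treatment cycles, at Day 22 of Cycles 1 and 2, and at the EOT/C8D1 visit. A patient who forgets the tablets on Day 1 and brings them on Day 8 should have a recorded count, yet the Note as written still excludes the cycle.

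Tolerability is part of the primary objective, and the other planned summaries do not measure the amount of drug taken. Exposure is last dosing day minus first dosing day plus 1, so days on hold count as exposed. Disposition counts patients with interruptions or reductions. The SAP plans no dose-intensity summary. Per-cycle compliance is thus the closest planned summary of Tenalisib actually taken.

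**Working it through.** The documents give no compliance rate, no non-return rate and no sample-size figure tied to compliance, so there is no planned figure to reproduce. The bias can be written down and illustrated.

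**Formula.** Let f be the share of patient-cycles not returned on schedule, cR the mean compliance in returned cycles and cN the true mean in unreturned cycles.

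- Reported mean = cR
- True mean = (1 − f) × cR + f × cN
- Bias = reported − true = f × (cR − cN)

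The bias is positive only if cN is below cR. It is zero if they are equal and negative if non-returners are more adherent.

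**Inputs.** Twelve patients in a cycle is the planned expansion group size (Protocol 9.2). The values cR = 95%, one to four unreturned cycles, and each cN below are assumptions.

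| Unreturned of 12 | True mean if cN = 50% | Bias, cN = 50% | Bias, cN = 80% | Bias, cN = 95% | Bias, cN = 100% | Bias, cN = 0% |
|---|---|---|---|---|---|---|
| 1 | (11×95 + 50)/12 = 91.25% | +3.75 | +1.25 | 0 | −0.4 | +7.9 |
| 2 | (10×95 + 100)/12 = 87.5% | +7.5 | +2.5 | 0 | −0.8 | +15.8 |
| 3 | (9×95 + 150)/12 = 83.75% | +11.25 | +3.75 | 0 | −1.25 | +23.75 |
| 4 | (8×95 + 200)/12 = 80.0% | +15.0 | +5.0 | 0 | −1.7 | +31.7 |

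Biases are in percentage points. The last two columns are the best and worst cases. With two unreturned cycles, for example, the true mean lies between 950/12 = 79.2% and (950 + 200)/12 = 95.8%, against a reported 95%.

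**Small cohorts.** With 3 to 6 patients per escalation cohort, one excluded patient is 1/3 = 33% to 1/6 = 17% of the cell.

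**Which direction is more plausible.** Protocol 5.5.1 asks only for unused drug, so a fully adherent patient with nothing left might be recorded as a non-return. Protocol 3.4.1 and 3.4.2 give 200 mg and 400 mg tablets in bottles of 30. If whole bottles are dispensed (an assumption), a full 28-day cycle leaves a surplus at each planned dose:

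- 400 mg BID as one 400 mg tablet: 56 of 60 used
- 600 mg BID as 200 mg + 400 mg: 56 of 60 of each strength used
- 800 mg BID as two 400 mg tablets: 112 of 120 used

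Under that assumption a fully adherent patient still has tablets to return, which makes upward bias more plausible. It does not establish it.

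**The case against.** A reader might infer that non-adherent patients and early leavers are excluded as classes. The documents do not support that. The rule acts on one return cycle and only on failure to return. A poor adherer who brings tablets back is counted, even below 80%. A patient who misses one return keeps all other cycles. Patients who leave early are due an EOT visit within 7 days of the last dose (Protocol 6.12), with drug compliance scheduled there.

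A reader might also infer that compliance is overstated as a matter of fact. Every input to the size is assumed, and the direction can reverse. Excluding unverifiable counts is also safer than treating unreturned tablets as taken, which would itself inflate the figure. Both objections stand.

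Nor is the gap wholly hidden. The per-cycle n is shown, SAP 14 lists study drug exposure and accountability separately, and SAP 10.1 reports dropouts with reasons. This stands in part. The n falls for non-return and for discontinuation alike, and non-returned cycles leave the compliance listing too. The compliance outputs therefore cannot separate the two, and a reader would have to rebuild the split from other listings.

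It can be said that the Note does not mention late returns. That is so, but its trigger is failure to return at the scheduled cycle and it makes no exception, so on its face a later count does not restore the cycle.

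Finally, compliance is not an endpoint, SAP 9.1 tests no hypothesis, and dose selection rests on DLTs and SRC judgement. This limits the importance of the point.

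**Conclusion.** The concern holds in a limited form. The Note makes the per-cycle Tenalisib summary conditional on scheduled return, which is plausibly related to adherence or early stopping, and the compliance outputs give no count of what was left out. Compliance may be biased, more plausibly upward. Neither size nor direction can be determined from the documents. On the assumed 12-patient, 95% illustration the bias runs from −1.7 to +15.0 points as unreturned cycles range from full adherence to 50%, and reaches +31.7 points only if four of twelve patients took nothing. No endpoint, hypothesis or sample size depends on it, and it does not show that any dose was taken less well than reported. It is a minor but worthwhile correction.

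**What to change.** Replace the Note in SAP 10.6.1 with three provisions:

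1. **Late returns.** When tablets come back after the scheduled cycle, compute compliance over the combined dispensing period (tablets dispensed minus tablets returned, divided by tablets due) and show it for the cycles covered.
2. **Never returned.** Keep the cycle in the listing, flagged as not returned/not documented. In the table, give the number of such patient-cycles next to the number of patients dispensed drug in each cycle. This separates non-return from discontinuation.
3. **Sensitivity.** Add a summary that uses documented missed doses, or best- and worst-case bounds. The share with documented compliance of at least 80%, over all patients dispensed drug, may serve as the worst case. It should not be the main figure, because the protocol uses 80% as a counselling trigger and this denominator counts undocumented cycles as failures.

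The cost is SAP wording and minor programming, with no new data collection. Late-return values would be derived rather than taken directly from the eCRF, and reported compliance may be slightly less favourable.
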